## **3. Methodology**

### **3.1 Study Design**

This design will be a retrospective cohort study. Clinical data of 107 T2DM patients enrolled in the SMBG clinic in Klinik Kesihatan Senawang from 1 January 2023 to 1 July 2023 (6 months) will be extracted from the electrical medical record (EMR). Patients who defaulted the follow up intervals will be excluded, as well as those without a repeated HbA1c. We will prepare a medical record abstraction form and collect demographics and clinical data. Demographic data included are patients' age and gender.

Clinical data collected will be baseline HbA1c and FBS at first visit and fourth visit (after six months). Data will be analyzed to compare the following: (1) the percentage of patients achieving reduction of HbA1c and FBS from baseline (2) Average reduction of HbA1c and FBS from baseline.

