## Research Synopsis

Study title	Analogy As A Possible Effective Consultation Tool In Type II Diabetes Mellitus Patients on Insulin: A Retrospective Cohort Study
Objective	To determine the effectiveness of a novel consultation tool & method based on analogies in improving glycemic control among type 2 diabetes patients on insulin
Study Design	
This design will be a retrospective cohort study. We have clinical data of 107 T2DM patients registered in a newly established SMBG clinic in Klinik Kesihatan Senawang from 1 January 2023 to 1 July 2023. These clinic sessions are conducted once a week, and use a new structured consultation tool based on an analogy to explain and consult these patients. Patients are followed up every 2 months. Their HbA1c will be measured after 3 sessions of consultations (6 months). Patients who defaulted the follow up will be excluded.
 
We will prepare a medical record abstraction form and collect demographics and clinical data from the EMR. Demographic

[figure not shown]
	data included are patients' age and gender. Clinical data collected will be baseline HbA1c and FBS at first visit and third visit (after six months). Data will be analyzed to compare the following: (1) the percentage of patients achieving reduction of HbA1c and Fasting Blood Glucose (2) Average reduction of HbA1c and Fasting Blood Glucose
Study endpoints/outcomes	Reduction of HbA1c and Fasting Blood Glucose levels after six months, after a minimum of 3 SMBG clinic visits.
Study Population	All patients enrolled and registered at the SMBG clinic in Klinik Kesihatan Senawang from 1 January 2023 to 1 July 2023.
Inclusion/Exclusion Criteria	
Inclusion criteria
 
 
1. Established T2DM patients, already on insulin therapy regardless of the type of insulin or regime or duration of treatment
 
2. HbA1c at referral more than 8.5%
 
3. Already seen by diabetic educator or dietitian prior to referral
 
4. Completed a minimum of 3 follow-ups under the SMBG Clinic
 
5. Has repeated HbA1c recorded at 3 follow-ups
 
 
Exclusion Criteria
 
 
1. Pregnant, or found to be pregnant during follow up
 

Sample Size	106 Subjects (universal sampling)
Study Duration	15 March 2024 - 15 June 2024 (3 Months)

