### **3.3 Inclusion Criteria**

1. Established T2DM patients, already on insulin therapy regardless of the type of insulin or regime or duration of treatment
2. HbA1c at referral more than 8.5%
3. Already seen by diabetic educator or dietitian prior to referral
4. Completed a minimum of 3 follow-ups under the SMBG Clinic
5. Has HbA1c recorded at 6 months

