## 3.6 Sample Size

106 patients. This study will use a universal sampling method. 106 patients were enrolled in the SMBG Clinic of Klinik Kesihatan Senawang from 1 January 2023 to 1 July 2023.

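### The enrolled count is 107 in two places and 106 in two others, and neither is the number that will be analysed once non-completers are excluded

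*Combined protocol and SAP*

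**What the plan says.** All references are to the combined protocol and SAP. Four places give a patient count:

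- Research Synopsis, Study Design row: "We have clinical data of 107 T2DM patients registered in a newly established SMBG clinic", for 1 January to 1 July 2023.
- Section 3.1: "Clinical data of 107 T2DM patients enrolled in the SMBG clinic", same dates.
- Research Synopsis, Sample Size row: "106 Subjects (universal sampling".
- Section 3.6: "106 patients were enrolled in the SMBG Clinic of Klinik Kesihatan Senawang from 1 January 2023 to 1 July 2023".

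Section 3.6 adds: "This study will use a universal sampling method". It gives no effect size, power or expected loss.

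Patients are then removed. The synopsis says "Patients who defaulted the follow up will be excluded", and section 3.1 says "Patients who defaulted the follow up intervals will be excluded, as well as those without a repeated HbA1c". Section 3.3 requires a referral HbA1c above 8.5% (criterion 2), "Completed a minimum of 3 follow-ups under the SMBG Clinic" (criterion 4) and an HbA1c at six months (criterion 5). Section 3.4 excludes pregnancy, including pregnancy found during follow-up. Section 3.9 plans a paired t-test or a Wilcoxon signed-rank test. Section 3.1 also plans the percentage of patients whose HbA1c and FBS fell, without naming its denominator.

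**The concern.** Two head counts of one closed cohort disagree. In a retrospective study that takes every patient in a fixed window, the cohort count is the starting point for every later number and should be exact.

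The second problem matters more. The figure offered as the sample size counts patients before exclusions, while the analysis can use only patients left after them. Two of the conditions, criteria 4 and 5, are met or failed after the consultation tool has been delivered. Staying in follow-up and having the outcome measured therefore decide who enters the cohort. If patients who stopped attending did worse, the percentage achieving reduction will look better than it was among all those given the consultation. Section 1.5 adds to this worry: it says HbA1c is repeated once the home glucose readings have been optimised. If practised that way, having a repeat value could itself depend on response.

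**Working it through.** **Step 1: can 106 and 107 both be right?**

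| Place | Count | Described as |
|---|---|---|
| Synopsis, Study Design row | 107 | registered |
| Section 3.1 | 107 | enrolled |
| Synopsis, Sample Size row | 106 | subjects, universal sampling |
| Section 3.6 | 106 | enrolled |

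One possible explanation is that 107 is the count before exclusions and 106 the count after. Section 3.6 rules this out by calling its 106 enrolled. Another is that 107 were registered and 106 enrolled. Section 3.1 rules that out by calling its 107 enrolled. Clinic and dates are the same, so at least one count is wrong. The documents do not show which.

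**Step 2: does the one-patient gap matter numerically?** There is no sample-size formula to reproduce. As a check, take a paired t-test at two-sided alpha 0.05 (section 3.9 gives 0.05 but not the sidedness, so two-sided is an assumption). The smallest mean change d, in SDs of the change, detectable with 80% power solves P(|T| > t(0.975, n−1)) = 0.80, where T is noncentral t with n−1 degrees of freedom and noncentrality d√n.

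- n = 107: d = 0.273
- n = 106: d = 0.275

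The gap is 1/106 = 0.9% of patients and has no practical effect.

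**Step 3: how many pairs will be analysed?** With N the verified enrolled count, the analysed number is N minus all exclusions, so it is at most N. No exclusion counts or default rate are given, so it cannot be derived. For scale only, starting from 107 with assumed losses (rounded down):

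| Assumed loss | Pairs | Detectable change at 80% power (SD) |
|---|---|---|
| 0% | 107 | 0.27 |
| 10% | 96 | 0.29 |
| 20% | 85 | 0.31 |
| 30% | 74 | 0.33 |
| 40% | 64 | 0.36 |
| 50% | 53 | 0.39 |

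Power falls slowly. FBS may have fewer pairs than HbA1c, because no criterion requires a repeat FBS.

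**Step 4: what does the choice of denominator do to the percentage?** Let E be the enrolled patients who met the baseline criteria, m those with a repeat value, and r those shown to have improved.

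- Completer percentage: p = r/m.
- Conservative bound, counting no repeat value as reduction not shown: r/E = p × (m/E).
- Opposite extreme, with every missing patient improved: (r + E − m)/E.

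The two extremes differ by (E − m)/E, the fraction lost. With an assumed 10%, 20% or 30% lost, the conservative figure is 0.9, 0.8 or 0.7 times the completer percentage, and the two extremes lie 10, 20 or 30 percentage points apart. This uncertainty is missing patients rather than sampling error, and no confidence interval from the completers reflects it.

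**The case against.** The best defence is that nothing here fails as a calculation. Under universal sampling no power target is needed, section 3.6 is a head count of the source cohort, and a difference of one patient is editorial. The exclusions are stated openly, and a paired test needs both values anyway. All of that stands, and it limits the point.

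A reader might infer several stronger things that the documents do not support:

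- **That the analysed number must be 106 or fewer.** This assumes 106 is the true enrolled count. If 107 is right, 107 is the ceiling.
- **That 106 is the planned denominator of the percentage.** No section says so. Because section 3.1 removes patients without a repeat HbA1c, the implied denominator is those who have one.
- **That precision is overstated.** No interval width or power is claimed, and a paired test uses the pairs actually present.
- **That marking withdrawal criteria as not applicable (section 3.5) conceals loss.** That entry suits a record review with no patient contact.

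It can also be objected that, as section 3.3 is written, a percentage over all eligible patients is simply the completer percentage, because criteria 4 and 5 are part of eligibility. That is correct, and the fix has to deal with it.

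**Conclusion.** The point holds in this form. The stated sample size is internally inconsistent, and neither 106 nor 107 is shown to be the number that will be analysed. The inconsistency itself is negligible in statistical terms. What deserves attention is that the analysed number is unstated and that entry depends on events after the intervention, so the percentage achieving reduction applies to completers and may be too favourable.

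The direction of that bias rests on an assumption that patients without a repeat value did worse. This is plausible but not shown. Its size depends on the fraction lost, which the documents do not give; the losses used above are illustrative. No corrected sample size can be offered from the text alone.

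**What to change.** 1. Recount the cohort from the EMR and use one enrolled number in all four places.
2. In section 3.6, label that number as enrolled or screened. Give the analysed number separately, for HbA1c and for FBS, in a flow table with a count for each reason: referral HbA1c of 8.5% or less, other baseline criteria not met, pregnancy (at entry and found later, on separate lines), defaulted, no repeat value.
3. In section 3.3, treat criteria 4 and 5 as conditions for the completer analysis, not for cohort entry. Without this change the next item has no effect.
4. Report the percentage achieving reduction twice: among completers, and over all enrolled patients who met the baseline criteria, with no repeat value counted as reduction not shown. Describe the second as a conservative bound, not as a best estimate.
5. Do not extend the mean change to non-completers by entering zeros, since that narrows the interval artificially. With an assumed SD of 1.5 points, mean change of 1 point, 74 pairs and 32 added zeros, the 95% half-width would be about 0.26, against 0.35 in the 74 pairs alone.

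The cost is a recount, a flow table and one extra percentage, all from existing records. The reported success percentage may be less favourable.

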### **3.2 Study Population**

All patients registered and enrolled to the SMBG clinic in Klinik Kesihatan Senawang during the period of 1 January 2023 to 1 July 2023

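### The before-after analysis keeps only patients who stayed and were retested, so both planned summaries are open to selection bias, and no analysis of the excluded patients is planned

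*Combined protocol and SAP*

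**What the plan says.** **Who is described.** Section 3.2 defines the population as "All patients registered and enrolled to the SMBG clinic in Klinik Kesihatan Senawang" during the first half of 2023. Section 3.6 says "This study will use a universal sampling method" and gives 106 as the number enrolled. Section 2 sets the aim as the effectiveness of the consultation tool in type 2 diabetes patients on insulin, with HbA1c and FBS both primary.

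**Who is analysed.** Section 3.1: "Patients who defaulted the follow up intervals will be excluded, as well as those without a repeated HbA1c". The Research Synopsis agrees: "Patients who defaulted the follow up will be excluded". Section 3.3 lists as inclusion criteria "Completed a minimum of 3 follow-ups under the SMBG Clinic" and "Has HbA1c recorded at 6 months". In the Synopsis the last criterion reads "Has repeated HbA1c recorded at 3 follow-ups".

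**When HbA1c is repeated.** The Synopsis says "Their HbA1c will be measured after 3 sessions of consultations (6 months"). Section 1.5, describing how the clinic runs, instead ties the repeat HbA1c to the point at which the patient's SMBG has been optimized, and gives no time.

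**What is planned.** Section 3.9 contains descriptive statistics, the paired t-test and the Wilcoxon signed-rank test. Section 3.1 names two summaries for each outcome: the percentage with a reduction and the average reduction.

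**The concern.** Whether a patient keeps attending and is retested is settled after the first visit and may be related to how that patient's glucose responds. If so, an average over those who stayed differs from the average over those who started, and a paired test cannot detect the difference. The objective is worded for the wider group, so a completer result could be read as the effect in everyone enrolled. With no flow from enrolled to analysed, no comparison of included with excluded patients and no sensitivity analysis, a reader could not tell whether the gap is negligible or material.

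FBS has an additional gap. It is a primary outcome, but no criterion or rule covers a missing repeat FBS, so the FBS analysis may rest on yet another subset.

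**Working it through.** **Step 1. Sort the entry conditions by when they become known.**
- At or before the first visit: type 2 diabetes already on insulin, HbA1c above 8.5% at referral, and already seen by an educator or dietitian (criteria 1 to 3).
- Only afterwards: no default, at least three follow-ups, and a repeat HbA1c (criteria 4 and 5 and the Section 3.1 exclusions).

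The second group creates the opening for bias.

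**Step 2. The mean.** Let N be the number eligible at baseline, n the number analysed, m_a the mean reduction among the analysed and m_x the mean among the lost.

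- Mean over all eligible = [n × m_a + (N − n) × m_x] / N
- Analysed mean minus mean over all eligible = [(N − n)/N] × (m_a − m_x)

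The difference is zero if n = N or if m_a = m_x. The documents give no n, m_a or m_x, so its size and sign cannot be derived. The following is illustration only. It takes every enrolled patient as eligible and assumes m_a = 1.0 HbA1c point:

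| Analysed | Lost: no change | Lost: worse by 0.5 | Lost: reduced by 2.0 |
|---|---|---|---|
| 85 of 106 | 85/106 = 0.80 | (85 − 10.5)/106 = 0.70 | (85 + 42)/106 = 1.20 |
| 106 of 107 | 106/107 = 0.991 | (106 − 0.5)/107 = 0.986 | (106 + 2)/107 = 1.009 |

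The last column shows that understatement is possible too.

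**Step 3. The percentage with a reduction.** These bounds need no model of why patients were lost. They assume that about 80% of analysed patients reduce.
- 85 of 106 analysed, 68 reduce, 21 lost: lowest 68/106 = 64.2%; highest (68 + 21)/106 = 84.0%.
- 106 of 107 analysed, 85 reduce, 1 lost: lowest 85/107 = 79.4%; highest 86/107 = 80.4%.

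The point is minor or serious depending on a retention figure that the documents do not state.

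**Step 4. Timing of the repeat HbA1c.** Section 1.5 and the six-month rule in the Synopsis and Sections 3.1 and 3.3 are not clearly consistent. If Section 1.5 governed practice, having an outcome could depend on response, in either direction. Patients not yet optimized might have no repeat value. Patients optimized early might be retested before six months or before three follow-ups, and so fail criterion 4 or 5. The visible text does not define optimized, and Figure 1 is not shown in the text reviewed.

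**Step 5. Other passages to reconcile.** None of these is evidence of bias.
- Number: 107 in the Synopsis design text and Section 3.1; 106 in the Synopsis sample size and Section 3.6. Sections 3.1 and 3.6 both call their figure enrolled, and no analysed number is given.
- Follow-up value: third visit in the Synopsis, fourth in Section 3.1, both at six months. With visits every two months from month 0, the third falls at month 4 and the fourth at month 6, so this may only be a difference in counting.
- First review: 6 weeks in the first-visit contents list (Figure 2); two months in Section 1.5 and the Synopsis. This bears on what counts as defaulting a follow-up interval.

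**The case against.** The strongest reply is that the restriction is openly declared. A source population narrowed by criteria is ordinary protocol structure, universal sampling can mean taking everyone who meets the criteria, and the Synopsis builds a minimum of three clinic visits into the endpoint itself. This largely stands: nothing is concealed, and a reader who infers that universal sampling contradicts the inclusion criteria goes too far. What remains is that the objective is worded more broadly than the completer endpoint, and that losses are not accounted for.

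Second, perhaps nobody was lost. That is possible, and the bias would then be zero. The documents do not say whether 106 or 107 is a count before or after exclusions. For the same reason, reading 107 and 106 as one patient lost is not supported.

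Third, the Section 1.5 sentence is background prose that leads to a figure not visible here, and the data rules lie elsewhere. This stands, so that mechanism is only conditional.

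A reader might also infer that the reductions are biased, and biased upwards. Overstatement is the more plausible direction if those who left or were not retested did worse, but the documents contain nothing on how they fared. Neither the presence of bias nor its direction is established.

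Finally, a participant flow is partly a matter for the report, and without a comparator even a full-cohort change would not establish effectiveness. Both are fair. They limit what the fix can achieve but do not remove the reason for it.

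**Conclusion.** The point holds in this form: the analysis set is defined by post-baseline attendance and retesting, the objective is wider, and the plan offers no means of judging the difference. Both planned summaries are therefore open to selection bias. The magnitude is not derivable; every figure in the illustrations except the counts 106 and 107 is assumed or computed from assumed inputs, and none of them supports a severity rating. The point should be fixed because the omission touches both summaries of both primary outcomes and is cheap to repair. Confidence is medium, since retention is unknown and the loss may be trivial.

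**What to change.** 1. Reconcile the timing of the repeat HbA1c (Section 1.5 against the Synopsis and Sections 3.1 and 3.3), the third with the fourth visit, the 6-week with the two-month review, and 106 with 107.
2. Do not require attendance. Analyse every non-pregnant patient meeting criteria 1 to 3 who has an HbA1c in the EMR within one stated window around six months after the first visit, and do the same for FBS with its own count. Report the current completer set alongside. Either set may be labelled main.
3. Both sets still condition on having been retested, so add sensitivity analyses over all eligible patients. For the mean, assume no change and then worse than baseline in those without a value. For the percentage, count them as non-reducers and give best and worst bounds.
4. Compare baseline HbA1c, FBS, age and gender of included and excluded patients. Give the flow from one enrolled number to the number analysed for each outcome, with reasons for each loss.
5. If the results differ materially, or the excluded records cannot be reopened, limit the conclusion to retained and retested patients.

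**Cost.** SAP wording, extra abstraction from the same EMR and a few simple analyses. Section 3.13 says the data were anonymized before extraction, so returning to excluded records may need re-linkage (Section 3.14 describes a study identification number) or ethics review. If retesting followed Section 1.5, some six-month values may not exist. The estimate may be less favourable; if few were lost, it will barely move and the flow will show why. None of this supplies a comparator.

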- 1.4. In clinical practice, analogies are recognized as valuable tools for facilitating communication while enhancing doctor-patient interactions, particularly in elucidating complex medical concepts. It is widely used in oncology to communicate with patients about their current condition. When presented in vignette form, analogies have demonstrated a potential for increasing objective comprehension among patients. They offer a means for simplifying intricate medical concepts, thus improving patient comprehension and engagement, ultimately leading to better health outcomes. This represents a promising approach to enhancing doctor-patient communication in a very complex disease like T2DM. However, the effectiveness of analogies may vary depending on the complexity of the medical issue and the numeracy level of the individual, highlighting the importance of tailoring analogies to suit the needs and cultural context of the patient.
- 1.5. Hence, we developed a consultation tool based on the “Garbage, lorry, factory” analogy. In this analogy, the garbage represents glucose, the lorry represents insulin, and the factory represents the muscle. We tested this method through a

specialized clinic in Klinik Kesihatan Senawang, Negeri Sembilan from January 2023, where patients are referred to a 2-monthly consultation with primary care doctors. On the very first visit, patients are clerked to provide baseline background information. Then, they will be presented with the “Garbage and Lorry” analogy, assisted by a visual tool (Appendix 1), to explain the pathophysiology of T2DM. The presentation includes detailed lifestyle modification advice like diet, exercise, sleep. It ends with an explanation of the pharmacology of the common T2DM drugs and insulin, all guided by the same analogy. At the end of the consultation, patients would be given an insulin intensification protocol built based on Malaysia’s local guidelines that they would have to follow, and was given a follow up after 2 months, with a 4-point SMBG chart to be monitored a week before. The follow up would be reviewing the SMBG, and optimizing their insulin regime based on the blood glucose profile. Once their SMBG is optimized, their HbA1c is repeated. Figure 1 shows a flowchart of how the SMBG clinic runs.

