## **2. Objective**

To determine the effectiveness of a novel consultation tool based on analogies in improving glycemic control among type 2 diabetes patients on insulin with HbA1c and FBS as primary outcomes.

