### **3.4 Exclusion Criteria**

1. Pregnant or found to be pregnant during follow-up

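### Changes in other glucose-active treatment are neither recorded nor restricted, so they are absorbed into the reduction credited to the consultation tool

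*Combined protocol and SAP*

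**What the plan says.** The data to be extracted are listed in section 3.1, and the Research Synopsis gives the same variables. For demographics: "Demographic data included are patients' age and gender". For clinical data: "Clinical data collected will be baseline HbA1c and FBS at first visit and fourth visit (after six months". Neither place lists a drug, a dose or a steroid course.

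Section 3.4 has one exclusion: "Pregnant or found to be pregnant during follow-up". Section 3.1 adds two more, neither concerning drugs: "Patients who defaulted the follow up intervals will be excluded, as well as those without a repeated HbA1c". The treatment criterion in section 3.3 is deliberately broad: "Established T2DM patients, already on insulin therapy regardless of the type of insulin or regime or duration of treatment".

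Section 1.5 describes the clinic. Of the first consultation it says: "It ends with an explanation of the pharmacology of the common T2DM drugs and insulin, all guided by the same analogy". Of later visits it says: "The follow up would be reviewing the SMBG, and optimizing their insulin regime based on the blood glucose profile".

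Section 2 makes HbA1c and FBS the primary outcomes, and its stated objective is "To determine the effectiveness of a novel consultation tool based on analogies in improving glycemic control among type 2 diabetes patients on insulin". Section 3.9 plans a paired t-test, or a Wilcoxon signed-rank test for non-normal data. It names no covariate, subgroup or sensitivity analysis.

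**The concern.** Each patient is compared only with his or her own baseline. Without a comparator group, treatment changes that happen alongside clinic attendance have nothing to balance against, and they enter both outcome summaries in full. These are the mean reduction and the percentage of patients with a reduction; the latter sets no minimum fall, so any decrease counts.

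A patient who starts a non-insulin agent between the two measurements, or whose baseline was raised by a steroid course that then ended, would be counted as improved by the consultation method. A patient who stops an agent or starts a steroid would be counted against it. As the extraction is planned, a reader of the results could not tell whether such changes were rare or common, or whether the reduction is also present in patients whose other treatment stayed the same.

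**Working it through.** **Is there a plan figure to reproduce?** No. The sample of 106 is a census of clinic enrolees (section 3.6), with no effect size, standard deviation or power behind it.

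**Step 1: could the plan deal with co-treatment anywhere?**

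| Possible safeguard | Where it would appear | What is there |
|---|---|---|
| Exclusion by drug | Synopsis, 3.1, 3.4 | Pregnancy, defaulting, no repeat HbA1c |
| Stable background treatment | Synopsis, 3.3 | Any insulin type, regimen or duration; nothing on other drugs |
| Recording | Synopsis, 3.1 | Age, gender, HbA1c, FBS |
| Adjustment or sensitivity analysis | 3.9 | None |
| Comparator group | 3.1, 3.9 | None; change from baseline only |

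All five are absent. Insulin dose is not extracted either, although insulin adjustment is the one drug change that section 1.5 describes.

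**Step 2: shift in the mean change.** If a share *f* of patients has an unrecorded treatment change that moves HbA1c by *d* points, the mean paired change moves by *f × d*. The documents give neither input, so these are assumptions: *f* from 10% to 40%, *d* from 0.5 to 1.0 points per added agent.

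- 0.10 × 0.5 = 0.05 and 0.10 × 1.0 = 0.10
- 0.20 × 0.5 = 0.10 and 0.20 × 1.0 = 0.20
- 0.40 × 0.5 = 0.20 and 0.40 × 1.0 = 0.40

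The range is 0.05 to 0.40 points. This does not depend on the number of patients.

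**Step 3: the sign can reverse.** If 20% gained an agent worth 0.5 points (shift 0.10) and another 10% had a change that raised HbA1c by 1.0 point (shift −0.10), the net is 0.10 − 0.10 = 0. If only the second group existed, the reduction would be understated by 0.10.

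**Step 4: could such a shift alone give a significant result?** Further assumptions: n = 106, two-sided 0.05 (section 3.9 does not state sidedness), SD of HbA1c change 1.0 to 2.0 points, true clinic effect zero. With SE = SD/√106, the smallest significant mean change is 1.96 × SE, which is 0.19, 0.29 and 0.38 points at SD 1.0, 1.5 and 2.0. The probability of significance is Φ(fd/SE − 1.96) + Φ(−fd/SE − 1.96).

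| Shift (points) | SD 1.0 | SD 1.5 | SD 2.0 |
|---|---|---|---|
| 0.05 | 8% | 6% | 6% |
| 0.10 | 18% | 10% | 8% |
| 0.20 | 54% | 28% | 18% |
| 0.30 | 87% | 54% | 34% |
| 0.40 | 98% | 78% | 54% |

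For example, at a shift of 0.30 and SD 1.5, SE = 0.146, fd/SE = 2.06, and Φ(0.10) is about 54%.

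The 106 are enrolees (the Synopsis and section 3.1 also say 107), and patients who default or lack a repeat HbA1c are dropped. With fewer patients analysed, these probabilities fall somewhat. No corresponding figure is offered for FBS or for the percentage with a reduction.

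**The case against.** The strongest reply is that these treatments may be part of what the clinic does. Its consultations are run by primary care doctors and cover the common diabetes drugs as well as insulin. The visible text describes insulin optimisation at follow-up, but it does not say that doctors left other drugs alone. The flowchart and the intensification protocol (Figures 1 and 3) could not be read in the text available here. This stands. A reader might infer that non-insulin drug changes lay outside the clinic package, so that restating the objective as the effect of the whole package would not help. The documents do not establish that. If the clinic made such changes, they belong to a package-level result, but they still confound the effect of the tool named in section 2. Recording them is useful either way.

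A second reply is that the size is entirely assumed. This also stands. A reader might infer that bias must run towards benefit, because patients enter with HbA1c above 8.5% and drug changes would then be additions. The documents give no frequencies and never mention steroids, and section 1.1 presents insulin as the step taken when oral agents become less effective.

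A third reply is that the missing comparator is the larger problem and that recording co-treatment does not cure it. That is correct. In patients with unchanged other treatment, insulin intensification and regression to the mean after selection on high HbA1c both remain. This limits what the remedy can show, but it does not make the missing data unimportant.

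**Conclusion.** The concern holds as a gap in data capture and interpretation. Other glucose-active treatment is neither restricted, recorded nor analysed, and a single-group paired comparison passes any change in it straight into both primary outcomes. That much follows from the text without assumptions.

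The size does not. The shift of 0.05 to 0.40 HbA1c points rests on assumed shares and assumed effects of added agents only. At the low end it is close to harmless; at the high end it could by itself produce a significant result. The net direction is unknown. The documents do not show that bias occurred.

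A reader might also infer that improvement should be claimed only if it is seen in patients with no treatment change. That goes too far. The subgroup is defined by events after baseline, may be selected on response, is smaller, and still contains the insulin and regression effects. It can support the interpretation but should not decide it.

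The change should be made: it is cheap and it alters what the study can conclude.

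**What to change.** 1. **Section 3.1 and the abstraction form.** Add the non-insulin glucose-lowering drugs, and the insulin regimen and dose, at the first and six-month visits. Add any systemic steroid course from 3 months before baseline to the repeat HbA1c. The Synopsis places the six-month measurement at the third visit and section 3.1 at the fourth; reconcile these so that the fields refer to one visit.
2. **Section 3.9.** Report how many patients had a change in each. Give the mean HbA1c and FBS change with 95% confidence intervals for patients with and without a change in non-insulin drugs or steroids. Label this a supportive sensitivity analysis, not a condition for the conclusion.
3. **Section 2 and reporting.** Describe the main result as change after clinic attendance, not as an effect of the analogy tool alone. State whether the clinic itself could change non-insulin drugs.

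The cost is some additional record extraction and one table; no patient is excluded and the main analysis stays as it is. Section 3.13 says that data were anonymised before extraction. If extraction is finished, a further query is needed, possibly through the study identification number in section 3.14. If the fields cannot be retrieved, state that as a limitation and keep the wording in item 3. The subgroup without a change will be smaller and is defined by post-baseline events, so its estimates will be less precise and must be read with caution.
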